### **Safety reporting to the DSMB**

Subjects may report safety issues with the study directly to the PI, any member of the PI's clinical and/or research teams, the MUSC Family Care Liaison, the IRB and/or ORI Director. In the absence of any such reports, the PI will systematically attempt to uncover any safety issues experienced by a subject during the approximate one week follow-up phone call. Any of the following will be reported to the DSMB if noted by the subject during the approximate one week follow-up phone call following SCS surgery (Aim 1): severe lower back or leg pain unresponsive to pain medication, repeated falls/imbalance, excessive bleeding from wounds, lower back irritation or bleeding around the site of paddle or IPG implant and/or return to the hospital. Any of the following will be reported to the DSMB if noted during the approximate 30-day return appointment (Aims 2 and 3): return to hospital, evaluation by another provider for findings related to spinal cord stimulation surgery, imaging, lab values and/or other reports indicating complications from spinal cord stimulation surgery. All the above-mentioned issues are outside of what would be reasonably expected for a normal postoperative course following spinal cord stimulation surgery. In accordance with HRPP Section 4.7, all the above-mentioned issues constitute adverse events and will be submitted to the DSMB for review (at 6 month intervals) in addition to being recorded in an adverse event log. In addition to serious adverse events, events that are unexpected, related or possibly related to a subject's participation in the research and suggests that the research places subjects or others at greater risk of harm than was previously known or recognized constitute Unanticipated Problems Involving Risks to Subjects or Others (UPIRSOs) and must be reported directly to the IRB (in addition to the DSMB). Finally, all deaths will be reported to the IRB within 24 hours of learning of the death, unless the death is expected (e.g., due to disease progression).

### **12.0 Withdrawal of Subjects**

Subjects may be withdrawn from the study without their consent, including stopping participation for safety reasons. For example, if at any point during the protocol it becomes evident that continuing with the study

Date: 8/1/19

Version: 01

would present risk in excess of that outlined in this document, data collection for that subject may be terminated. However, any data collected before the incident may still be used in analysis. At any time, subjects may also express desire to withdraw from the study. We will instruct the subjects that, to withdraw from the study, all they need to do is to contact one of the members of the study team and express the desire to be excluded from the study.

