The spinal cord relies on input from the motor cortex as well as sensory information from the extremities to carry out specific actions. For example, recent evidence suggests that preservation of temporally specific proprioceptive information via dorsal column primary afferent fibers is critical for motor behaviors such as ambulation. Since the spinal cord is exposed during the placement of the SCS device, information about a subject's motor and sensory spinal pathways can be easily obtained during the regular course of the procedure and compared to proprioceptive and motor responses once the subject is awake and moving with the device turned on. Our lab specializes in electrophysiological recordings in subjects undergoing spinal cord stimulator (SCS) implantation for CLBLP, while MUSC's Locomotion Laboratory specializes in quantifying proprioception and movement in human subjects. In this proposal, we will apply these techniques to subjects with CLBLP to determine effects of spinal neuromodulation on motor and sensory thresholds, proprioception, and kinematics. Our plan includes the following specific aims:

**Aim 1. Compare the effects of LFTS and HFBS on motor and sensory thresholds intraoperatively.** Question: Do HFBS waveform patterns modulate motor and sensory thresholds to allow more information to reach the spinal cord? In this aim, we will measure sensory and motor spinal thresholds in subjects undergoing SCS implantation during stimulation of epidural paddle contacts. *We hypothesize that HFBS will reduce motor and sensory thresholds relative to LFTS during epidural paddle activation.*

**Aim 2. Determine the effect of HFBS on proprioceptive afferent signaling from lower extremity muscle groups.** Question: Does HFBS, when compared to traditional LFTS, allow for increased spatial limb awareness during passive motion? In this aim, postoperative subjects from SA1 will undergo isokinetic passive proprioceptive testing before, during and after spinal cord stimulation with HFBS and LFTS parameters targeting musculature surrounding the knee. *We hypothesize that subjects will have increased awareness of the lower limb in space through passive movement during optimal HFBS compared to optimal LFTS parameters.*

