#### **5.0 Number of Subjects**

We propose to study 5 individuals with CLBLP. A prior study conducted by Formento et al, 2018 using SCS and proprioceptive testing published a standard error and 95% confidence interval using successful and unsuccessful SCS trial attempts ( $p < 0.05$  among LFTS parameters and no stimulation, with a minimum of 10 trials per stimulation setting). Based on this, we expect that our small population will exhibit similar variance. The subject sample size is in direct comparison to sample sizes of previous proof of concept studies regarding SCS for spinal cord physiology biomarker sampling. The research team plans to use a two-way repeated measures ANOVA model in order to investigate the varying differences in stimulation type and kinematic parameters. A Post hoc comparison will be made using a Tukey adjustment.

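### Use of a withdrawn subject's earlier data is optional, and the named repeated measures ANOVA drops anyone with a missing cell; with 5 subjects both rules need to be fixed in advance

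*Combined protocol and SAP*

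**What the plan says.** Section 5.0 (Number of Subjects) fixes the size: "We propose to study 5 individuals with CLBLP". It also contains the whole analysis plan, a "two-way repeated measures ANOVA model in order to investigate the varying differences in stimulation type and kinematic parameters", followed by "A Post hoc comparison will be made using a Tukey adjustment". The variance assumption is that "we expect that our small population will exhibit similar variance".

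The aims run in sequence in the same people. Under Aim 2 in section 1.0, "postoperative subjects from SA1 will undergo isokinetic passive proprioceptive testing", and Aim 3 draws on the subjects of the first two aims. Section 9.0, Step 2, places the proprioception session about 30 days after surgery. It has three stimulation conditions (HFBS, LFTS, none), at least 10 trials per condition, and testing before, during and after stimulation.

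Section 12.0 foresees two routes out. If the team ends data collection because of risk, "any data collected before the incident may still be used in analysis". A subject who wishes to leave need only "contact one of the members of the study team and express the desire to be excluded from the study"; the section does not say what happens to data already collected from that subject.

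The documents give no analysis set, missing-data method, replacement rule or sensitivity analysis. Section 11.0 has the DSMB reviewing a statistical analysis plan, but no fuller plan is in the documents.

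**The concern.** A subject can complete the operating-room measurements, or those and the proprioception session, and then stop. The completed data are valid for the aim they serve. Whether they enter the analysis rests on a permissive *may*, so nothing prevents the choice from being made after the results are known. With 5 subjects, one such choice carries weight.

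A subject can also stop within a session, for example after LFTS and no stimulation but before HFBS. A classical repeated measures ANOVA needs every subject-by-condition cell, so it would discard all of that subject's data for the aim, although section 12.0 permits their use. If stopping is related to a stimulation pattern, removing such subjects could also bias the HFBS-LFTS comparison.

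**Working it through.** **The plan's own figure.** N = 5 cannot be reproduced. Section 5.0 gives no effect size, standard deviation, power or study alpha; the 0.05 it mentions belongs to a cited earlier study.

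**Inputs.** From the documents: n = 5, three stimulation conditions, three phases. Assumed: two-sided alpha 0.05, normal errors, sphericity, a stimulation-by-phase (3 × 3) layout, and per-subject loss of 5% or 10%. The layout is an assumption because section 5.0 names the second factor only as kinematic parameters.

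**1. Losing one subject.**
- Paired 95% CI half-width, in SDs of the difference, is t(0.975, n−1)/√n. For n = 5: 2.776/√5 = 1.24. For n = 4: 3.182/√4 = 1.59. Ratio 1.28.
- Error df for the condition effect are (3−1)(n−1) = 8, falling to 6. Critical F rises from 4.46 to 5.14.
- The standardised paired difference (dz) detectable with 80% power rises from 1.68 to 2.13.
- In simulated three-condition ANOVAs (100,000 runs per effect size), removing one given subject changes the significance verdict in 18%, 22% and 15% of runs at dz = 1, 1.5 and 2, but in only 1% at dz = 3.

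**2. Keeping or dropping after seeing results.** Paired differences drawn from N(0,1), no true effect, smaller p-value reported (400,000 sets of 5):
- fixed rule: 4.9% (nominal 5%, within simulation error);
- one optional subject: 7.4%;
- two optional subjects: 11.5%.

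The omnibus F over three conditions gives 7.6% for one optional subject. If the subject left out is always the one with the lowest difference, the mean shifts by 0.29 SD.

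These rates apply only once a withdrawal has occurred. The chance of at least one loss is 1 − 0.95⁵ = 23% or 1 − 0.90⁵ = 41%. Treating any loss as one optional subject, always exploited, the overall rate is 0.77 × 5% + 0.23 × 7.4% ≈ 5.6%, or 0.59 × 5% + 0.41 × 7.4% ≈ 6.0%, and slightly more if double losses are counted.

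**3. One missing cell.** A 3 × 3 layout in 5 subjects has 45 cell means. With one cell missing, a standard repeated measures ANOVA routine stopped because the data were unbalanced. Dropping the subject leaves 4 × 9 = 36 cells; a mixed model uses 44.

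**4. Which mixed model.** The two-way ANOVA tests stimulation against the subject-by-stimulation term, on (2, 8) df. A model with only a random subject intercept uses the pooled residual, on (2, 32) df, so the tests differ even with complete, balanced data. Simulated false-positive rates with no true effect, n = 5 and residual SD 1:

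| Subject-by-stimulation SD | Two-way ANOVA | Random intercept only |
|---|---|---|
| 0.5 | 4.9% | 12.4% |
| 1.0 | 5.0% | 26.1% |

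**5. Precision recovered.** Take one value per condition, equal correlation, within-subject information only and unit error variance. The variance of HFBS−LFTS is 2/5 = 0.40 with five complete subjects and 2/4 = 0.50 with four. Now add a fifth subject with LFTS and no stimulation only. That subject's LFTS−none contrast has variance 2. In the four complete subjects that contrast has variance 0.50 and covariance −0.25 with HFBS−LFTS. The combined variance is 0.50 − 0.25²/(0.50 + 2) = 0.475. The share of the loss recovered is (0.50 − 0.475)/(0.50 − 0.40) = one quarter.

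**The case against.** The strongest reply is that the permissive wording reads naturally as permission to retain data rather than as an analysis rule. Consent pages were removed before review, and section 8.0 refers to a consent and HIPAA form that may cover data after voluntary withdrawal. Both points are fair. The second means that silence on voluntary withdrawal cannot be charged to the plan as an omission. Neither supplies an analysis rule in sections 5.0 or 12.0.

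Several stronger readings are tempting, and the documents do not support them:
- *An unblinded team decides case by case.* Section 9.0 describes blinding of the subject only, but nowhere do the documents say who decides on inclusion or what they know.
- *The two routes out are treated differently.* The visible text is silent on one route, and silence is not different treatment.
- *Subjects will mostly stop because of discomfort from stimulation.* Section 13.0 names discomfort and loss of balance as risks but does not say why subjects would withdraw. The hand switch stops the dynamometer arm and also records detection of movement; pressing it is not withdrawal.
- *No partly completed session can be analysed.* A cell with fewer than 10 trials can still be averaged. Only a wholly missing cell causes the loss, and only for the aim concerned.

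It is also right that 7.4% is a conditional worst case, and that most of the wider interval is the price of HFBS data never measured, which no model restores.

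**Conclusion.** The concern holds in limited form. Inclusion of earlier data is optional for one route out and unstated in the visible text for the other, and the named ANOVA discards subjects with a wholly missing cell. One optional subject with complete data for an aim could raise an assumed 5% error rate to at most about 7.4% in a paired comparison (7.6% for the three-condition F). Averaged over assumed loss rates of 5% to 10% per subject, the figure is nearer 5.6% to 6.0%. Losing one subject widens the paired interval by 28%. Such a choice or loss *can* change the conclusion at moderate effects; it need not, and it rarely would at very large ones. Alpha, effect sizes, loss rates and the 3 × 3 layout are assumptions, because the documents give none of them. The change is worth making because it is cheap and the study is small, not because the documents show selective inclusion.

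**What to change.** **Section 12.0.** Replace the permissive wording with a commitment: all data collected up to withdrawal, by either route, will be analysed for every aim for which they were obtained, subject to the consent terms and any request by the subject. Record the reason for stopping and the stimulation condition running at that moment.

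**Section 5.0.** Specify a linear mixed model with random subject, subject-by-stimulation and subject-by-phase effects (or subject by whichever second factor is used) and Kenward-Roger degrees of freedom. With complete, balanced data and non-negative variance estimates it matches the two-way ANOVA; otherwise it keeps partial subjects. Do not use a random subject intercept alone, which inflates error when subjects differ in their response to stimulation. Report results with and without incomplete subjects.

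**Cost.** A few sentences and a standard model routine, with no extra subjects or visits. At n = 5 the model may not converge, and the small-sample degrees of freedom must be specified. It recovers only part of the lost precision when the missing cell belongs to the HFBS-LFTS contrast (a quarter in the example above). It does not fully remove bias if stopping is related to stimulation, which is why the reasons for stopping and the paired sets of results are needed.

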### **13.0 Risks to Subjects**

All procedures will follow standard of care guidelines. Research staff will follow up with each participant by phone approximately one week after the surgical procedure, and during the approximate 30-day return, to make sure the participants are not having any problems. Nevertheless, this study still poses certain risks as outlined in the following sections:

**Surgical complication** – Due to the 15 extra minutes added to the surgery, connection of the paddle terminals outside the surgical field, and extra personnel in the room, there is a slightly increased risk of surgical infection. The extra risk of infection due to the research protocol does not increase this risk beyond the 1-5% overall historical risk of complications from the SCS surgical procedure.

#### **TTDPM**

While testing for proprioception retention of the lower extremities, subjects may encounter discomfort due to non-volitional muscle activation that hinders passive movement. To mitigate this risk, the Biodex system has a subject-controlled trigger that immediately stops the dynamometer's passive motion and may be activated at any time a subject experiences discomfort or pain during the test.

#### **Overground and Treadmill Walking**

Subjects will be asked to walk on a pressure sensitive mat at self-selected walking speeds and on a treadmill at self-selected walking speeds with each scenario having the subject in an upper thoracic safety harness which is tethered to the ceiling for fall protection. Despite the aforementioned safety measures, there still exists a risk of loss of balance, fall and potential injury. The risk to subjects through these tasks do not exceed risks involved with general physical therapy settings and may result in mild muscle fatigue or discomfort that generally subsides within a few days. Subjects will be given ample rest time and may have additional rest time at any point throughout data collection periods. Furthermore, subjects will be assisted during large movements or during potential transfers across different surfaces by an IRB-approved study member.

#### **Photography and videography**

Subjects will be videotaped during performance of supine / walking SCM and EMG modulating protocols. We will also photograph and/or videotape any other aspect of the subject's research participation that will help us correlate the subject's condition with the EMG and kinematic data. The videos and photos we record can include the full face, upper body, arms, and legs. Photography and videography carry a risk of loss of privacy. Photos and videos will be stored on a secure server. Only approved study personnel will have access to these files.

#### **Loss of Confidentiality**

Additional risks include loss of confidentiality. To mitigate this risk, a linking database associating the participant ID and subject identifiers will be maintained separately from the research data on a password protected server and only IRB-approved personnel will have access to the linking database.

### **14.0 Potential Benefit to Subjects or Others**

This research is not expected to provide direct benefit to individual subjects, though it may lead to improvements in care for patients suffering from chronic pain in the future. A successful study outcome may contribute to this improvement and may be used in future subjects undergoing similar procedures.

Date: 8/1/19

Version: 01

## 15.0 Sharing of Results with Subjects

Due to the extensive amount of time needed for data processing, it will not be possible to disclose individual study results to subjects or their healthcare providers. Incidental findings and other results of diagnostic tests associated with routine care of subjects will be shared with the subject and their physician by phone, writing and/or electronic medical record communication by the PI.

## 16.0 Drugs or Devices

All of the following medical devices are to be used as they are FDA approved and marketed.

The LR10 (Tucker Davis Technologies, Alachua, FL), used for signal recording from SCS paddle during MEP and SSEP procedures is a non-diagnostic physiological signal amplification device. The device is exempt from Investigational device exemptions (IDE) regulation per 21 CFR 812.2 paragraph C (*exempted investigations*) subparagraph 3. (please see 21\_CFR\_812.2\_Exempt\_Devices.pdf)

The Bidex Pro System 4 (Biodex Medical Systems, Shirley, NY), used during the TTDPM testing, is an upgraded version of a previous Isokinetic dynamometer (Biodex System 3) that was also classified as a 510K/Pre-market notification device (K951770). Due to the similar nature and intent of use for the upgraded model, the Bidex Pro System 4 is exempt from 510K classification as per 21 CFR 890 Subpart A and 21 CFR 890 Subpart B 890.1925 *Isokinetic testing and evaluation system classification*. (please see 510(k)\_Biodex System 3\_Biodex Medical.pdf , 510(k)\_PremarketExemption.pdf)

The MA300 EMG system (Motion Labs, Baton Rouge, LA), used during EMG module analysis, is a 510K/Pre-market notification device (K974385) as described in 21 CFR 807 Subpart E (please see 510(k)\_MotionLabs\_EMG.pdf)

